2.8.1.2 FACT-HN

The FACT-H&N contains 12 items (hn1 to hn12, i.e. q28, to q39). The H&N subscale score is calculated by the corresponding formula below:

Item 2, 3, 6, 12 will be calculated in reverse scale:

$$\text{hn2} = 4 - \text{hn2}$$

$$\text{hn3} = 4 - \text{hn3}$$

$$\text{hn6} = 4 - \text{hn6}$$

$$\text{hn12} = 4 - \text{hn6}$$

Both hn8 (i.e. q35) and hn9 (i.e. q36) are not currently scored.

Score=missing if number of above questions not answered is greater than 5; Otherwise,
Score = $(\text{Total for the answered questions} / \text{Total questions answered}) * 10$

The range of H&N scale score is 0 to 40. Trial Outcome index (TOI) for FACT-H&N is calculated by (PWB + FWB + H&N).

Overall FACT-H&N score is calculated by (FACT-G total + H&N).

2.8.1.3 MDADI

The MDADI consists of 20 items, one global item (scored individually) and 19 items organized into domains: emotional (6), physical (8) and functional (5). Each item is scored on a 1-5 scale (Two items have their scores reversed, E7 and F2; for all others, 5 points are given for “strongly disagree”).

Global item: Question: 1

Score=missing if number of above question is not answered; Otherwise,
Score = (Score for question one - 1)*100/4

Emotional scale: Question: E1 to E6

Score=missing if number of above questions not answered is greater than 3; Otherwise,
Score = ((Total for the answered questions/Total questions answered)-1)*100/4

Physical scale: Question: P1 to P8

Score=missing if number of above questions not answered is greater than 4; Otherwise,
Score = ((Total for the answered questions/Total questions answered)-1)*100/4

Functional scale: Question: F1 to F5

Score=missing if number of above questions not answered is greater than 2; Otherwise,
Score = ((Total for the answered questions/Total questions answered)-1)*100/4

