GE6	I worry that my condition will get worse.....	0	1	2	3	4

FUNCTIONAL WELL-BEING		Not at all	A little bit	Some-what	Quite a bit	Very much
GF1	I am able to work (include work at home).....	0	1	2	3	4
GF2	My work (include work at home) is fulfilling.....	0	1	2	3	4
GF3	I am able to enjoy life.....	0	1	2	3	4
GF4	I have accepted my illness.....	0	1	2	3	4
GF5	I am sleeping well	0	1	2	3	4
GF6	I am enjoying the things I usually do for fun	0	1	2	3	4
GF7	I am content with the quality of my life right now	0	1	2	3	4

This box to be completed by the clinical research associate: Pt. Serial #: _____ Pt. Initials: _____

FACT-H&N (Version 4)

By circling one (1) number per line, please indicate how true each statement has been for you during the past 7 days.

ADDITIONAL CONCERNS		Not at all	A little bit	Some-what	Quite a bit	Very much
H&N 1	I am able to eat the foods that I like	0	1	2	3	4
H&N 2	My mouth is dry	0	1	2	3	4
H&N 3	I have trouble breathing	0	1	2	3	4
H&N 4	My voice has its usual quality and strength	0	1	2	3	4
H&N 5	I am able to eat as much food as I want	0	1	2	3	4
H&N 6	I am unhappy with how my face and neck look.....	0	1	2	3	4
H&N 7	I can swallow naturally and easily	0	1	2	3	4
H&N 8	I smoke cigarettes or other tobacco products.....	0	1	2	3	4
H&N 9	I drink alcohol (e.g. beer, wine, etc.)	0	1	2	3	4
H&N 10	I am able to communicate with others	0	1	2	3	4
H&N 11	I can eat solid foods.....	0	1	2	3	4
H&N 12	I have pain in my mouth, throat or neck	0	1	2	3	4

Please check to make sure you have answered all the questions.

Please fill in your initials to indicate that you have completed this questionnaire: _____

Today's date (Year, Month, Day): _____

Thank you.

MDADI

Quality of Life Questionnaire – ENGLISH

CCTG Trial: **HN.10**

This **page** to be completed by the Clinical Research Associate

Patient Information

CCTG Patient Serial No: _____

Patient Initials: _____

(first-middle-last)

Institution: _____

Investigator: _____

Scheduled time to obtain quality of life assessment: please check (✓)

Prior to registration Last week of radiotherapy

Post Radiotherapy Treatment, Prior to Progression

month 3 month 6 month 12 month 24 month 36

The FACT-H&N questionnaire should be completed before the MDADI, EQ-5D-5L, PRO-CTCAE and Lost Productivity Questionnaire (when applicable).

Were ALL questions answered? Yes No If no, reason: _____

Was assistance required? Yes No If yes, reason: _____

Where was questionnaire completed: home clinic another centre

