Comments: _____

Date Completed: _____ - _____ - _____
 yyyy mmm dd

*PLEASE ENSURE THIS PAGE IS FOLDED BACK BEFORE HANDING
TO THE PATIENT FOR QUESTIONNAIRE COMPLETION.*

CCTG use only

Logged: _____

Study Coord: _____

Res Assoc: _____

Data Ent'd: _____

Verif: _____

_____ - _____ - _____

_____ - _____ - _____

_____ - _____ - _____

_____ - _____ - _____

_____ - _____ - _____

The M. D. Anderson Swallowing Inventory (MDADI)

This questionnaire asks for your views about your swallowing ability. This information will help us understand how you feel about swallowing.

The following statements have been made by people who have problems with their swallowing. Some of these statements may apply to you.

Please read each statement and circle the response which best reflects your experience in the past week.

	Strongly Agree	Agree	No opinion	Disagree	Strongly Disagree
My swallowing ability limits my day to day activities					
E2. I am embarrassed by my eating habits	Strongly Agree	Agree	No opinion	Disagree	Strongly Disagree
F1. People have difficulty cooking for me	Strongly Agree	Agree	No opinion	Disagree	Strongly Disagree
P2. Swallowing is more difficult at the end of the day	Strongly Agree	Agree	No opinion	Disagree	Strongly Disagree
E7. I do not feel self-conscious when I eat.	Strongly Agree	Agree	No opinion	Disagree	Strongly Disagree
E4. I am upset by my swallowing problem.	Strongly Agree	Agree	No opinion	Disagree	Strongly Disagree
P6. Swallowing takes great effort.	Strongly Agree	Agree	No opinion	Disagree	Strongly Disagree
E5. I do not go out because of my swallowing problem.	Strongly Agree	Agree	No opinion	Disagree	Strongly Disagree
F5. My swallowing difficulty has caused me to lose income.	Strongly Agree	Agree	No opinion	Disagree	Strongly Disagree
P7. It takes me longer to eat because of my swallowing problem	Strongly Agree	Agree	No opinion	Disagree	Strongly Disagree

This box to be completed by the clinical research associate:

Pt. Serial #: _____ Pt. Initials: _____

P3. People ask me, "Why can't you eat that?"	Strongly Agree	Agree	No opinion	Disagree	Strongly Disagree
E3. Other people are irritated by my eating problem.	Strongly Agree	Agree	No opinion	Disagree	Strongly Disagree
P8. I cough when I try to drink liquids.	Strongly Agree	Agree	No opinion	Disagree	Strongly Disagree
F3. My swallowing problems limit my social and personal life.	Strongly Agree	Agree	No opinion	Disagree	Strongly Disagree

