2.8.2.3 Cross-sectional analysis

The mean and standard deviation of QOL scores at baseline and mean and standard deviation of QOL change scores from baseline at each assessment time will be calculated.

Summary statistics of baseline score for each domain in FACT-HN and MDADI will be summarized in Table 19. Mean QOL change score from baseline for each assessment time will be summarized in Table 20.

2.8.3 Analysis of FOIS and PSS-HN.

FOIS and PSS-HN are not a patient reported outcome however it is an important investigator-completed assessment of swallowing function and have been included in HN10. “Compliance” does not apply, and MID is not well defined for FOIS and PSS-HN. Thus, only the cross-sectional analysis specified in 2.8.2.3 will be conducted for both.

Cross-sectional analysis results related to FOIS and PSS-HN will be summarized in Table 21.

Figure 1. KM for EFS

Figure 2. KM for OS

Figure 3. KM for LRC

Figure 4. KM for out-of-field regional control

Figure 5. KM for DMFS

Figure 6. Boxplots for FACT domain score changes from baseline by assessment time

Figure 7. Boxplots for MDADI domain score changes from baseline by assessment time

Figure 8. Boxplots for FOIS domain score changes from baseline by assessment time

Figure 9. Boxplots for PSS-HN domain score changes from baseline by assessment time

Table 1. Accrual by center

Data set: All Patients

	Number of patients (%)	
	Total N = ***	
Canada	*** (**)	
Center #1	*** (**)	
Center #2	*** (**)	
...	*** (**)	
...		

Table 2. Eligibility and reasons for ineligibility

Data set: All Patients

	Number of patients (%)	
	Total N = ***	
Eligible/Evaluable	*** (**)	
Not Eligible/Inevaluable	*** (**)	
Major protocol violation		**
<violation type 1>		**
<violation type 2>		
...		

Table 3. Baseline patient characteristics

Data set: All Patients (N = 103)	
	Total N = 103
Age (years)	
N	
Median (Min-Max, Q1-Q3)	
Mean (SD)	
≥ 65	
<65	
Sex	
Female	
Male	
ECOG Performance Status	
0	
1	
T Stage	
T1	
T2	
T3	
T4 ¹	
N Stage	
N0	
N1	
N2 ²	
Primary site	
Base of tongue	

Tonsil	
Soft palate	
Smoking history	
No smoking ever	
Smoked ever	
Greater than 100 cigarettes during lifetime	
100 or fewer cigarettes during lifetime	
Pipe or cigar smoker only	
Length of smoking in years	
N	
Median (Min-Max, Q1-Q3)	
Mean (SD)	
Current smoking	
Yes	
No	
Unknown or not answered	
Current average number of cigarettes smoked per day	
N	
Median (Min-Max, Q1-Q3)	
Mean (SD)	

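### Two quality-of-life scoring rules in the SAP are wrong as written: the MDADI emotional scale uses E1 to E6 although the form has E2 to E7, and FACT-H&N item 12 is computed from item 6

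*SAP*

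**What the plan says.** **MDADI.** SAP 2.8.1.3 describes one global item and "19 items organized into domains: emotional (6), physical (8) and functional (5"). It adds: "Two items have their scores reversed, E7 and F2". It then gives the rule for the emotional domain as "Emotional scale: Question: E1 to E6", with the score set to missing when more than three items are unanswered. The form in Protocol Appendix V has emotional items E2, E3, E4, E5, E6 and E7. One of them reads "E7. I do not feel self-conscious when I eat". No item is labelled E1, and the global item has no label.

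**FACT-H&N.** SAP 2.8.1.2 states: "Item 2, 3, 6, 12 will be calculated in reverse scale". The lines for hn2, hn3 and hn6 each subtract the item itself from 4. The line for hn12 subtracts hn6. Items 8 and 9 are not scored, the mean of the answered items is multiplied by 10, and the section adds: "The range of H&N scale score is 0 to 40". On the form, item 12 is "I have pain in my mouth, throat or neck", while item 6 asks about unhappiness with the look of the face and neck.

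**Use of the scores.** Baseline scores go to Table 19. SAP 2.8.2.3 adds: "Mean QOL change score from baseline for each assessment time will be summarized in Table 20". Figures 6 and 7 show the changes as boxplots.

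**The concern.** Each rule conflicts with the text around it and with the form that patients complete. The MDADI rule names an item that does not exist and omits one that the same paragraph takes care to reverse. The FACT-H&N rule announces a reversal of item 12 and then never uses item 12.

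These are the operative scoring rules for two instruments that serve the quality-of-life and subjective-swallowing secondary objectives. MDADI is the only patient-reported, swallowing-specific instrument that the SAP scores; FOIS and PSS-HN are completed by the investigator. The trial has one arm, so no comparison group scored the same way would offset an error. Change from baseline does not remove it either, unless the mis-scored items move together. Pain in the mouth, throat or neck is directly relevant to patients having radiotherapy there, and the last week of RT is a scheduled assessment.

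**Working it through.** **1. Reproduce the SAP's own figures**

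- MDADI items counted on the form: E2 to E7 (6), P1 to P8 (8), F1 to F5 (5), one global. 6 + 8 + 5 + 1 = 20, as the SAP says. The physical and functional lists in the SAP match the form. The emotional count of 6 is reached only with E2 to E7; E1 to E6 matches five form items.
- H&N subscale: 12 items less the two unscored leaves 10. Each runs from 0 to 4, so the range is 0 to 40. This agrees with the SAP when item 12 is reversed from itself.

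**2. MDADI emotional scale, complete form**

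The score is (mean - 1) x 100/4. Let m be the mean of E2 to E6 and e the recoded E7.

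- Correct mean: (5m + e)/6. Mean as written: m.
- Error (as written minus correct): 25 x [m - (5m + e)/6] = 25 x (m - e)/6.
- Extreme case: m = 5 and e = 1 gives 25 x 4/6 = 16.7 points (100.0 instead of 83.3). The mirror case gives -16.7.
- The error is zero only when e equals m, which happens in 625 of the 15,625 possible answer sets.

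**3. MDADI emotional scale, missing items**

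E1 is taken as always unanswered, because the form has no such item.

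- Patterns scorable with at most three of E2 to E7 blank: 1 + 6 + 15 + 20 = 42.
- As written, the score is missing once three of E2 to E6 are blank. When E7 is answered, that is one blank item too soon.
- Scorable patterns lost: three of five blank with E7 answered, C(5,3) = 10 of the 42.
- When E7 is blank, the limit falls in the same place under both rules.

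**4. FACT-H&N, using the raw item 6**

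- Correct contribution of items 6 and 12: (4 - hn6) + (4 - hn12). As written: (4 - hn6) + (4 - hn6).
- Error on a complete form: hn12 - hn6, from -4 to +4 points. It is non-zero for 20 of the 25 answer pairs and zero for the 5 in which the two answers are equal.
- With n of 10 items answered, both of these among them, the limit is 4 x 10/n = 40/n. At n = 5, the fewest the SAP allows, this is 8 points.
- TOI (PWB + FWB + H&N) and the FACT-H&N total (FACT-G + H&N) inherit the same error.
- Error in a mean change, complete forms: mean change in hn12 minus mean change in hn6. Illustration with assumed answers: hn6 goes from 0 to 1 and hn12 from 0 to 3. The correct change is -1 - 3 = -4; as written it is -1 - 1 = -2.

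**5. FACT-H&N, running the lines in printed order**

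If hn6 has already been reversed, hn12 becomes 4 - (4 - hn6) = hn6, so the two items always sum to 4. The other eight items contribute 0 to 32, so complete forms run from 4 to 36, against the SAP's 0 to 40. A symptom-free patient scores 36. This reading does not rescue the line.

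**6. Volume**

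At most 99 eligible patients x 7 assessments = 693 forms could be scored by each rule.

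**The case against.** The best reply is that the SAP carries its own correction. It gives six emotional items and a reversed E7; it lists item 12 among the reversed items and states a 0 to 40 range. A programmer working from the form would probably notice that E1 is absent, and nothing shows that the literal lines were coded. No decision depends on these scores: Protocol 13.6 and SAP 2.8.2.3 plan only descriptive summaries, with no QOL test, responder threshold or power claim. On this view the slips are editorial.

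Most of that is true and limits the weight of the point. It does not make the lines right. Coded literally, they give wrong scores; coded correctly, the program departs from the SAP without a record.

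The sizes also need to be read with care, and this part of the objection stands. The 16.7 and 8 points are extremes, and the counts of answer pairs and missing-item patterns are not error rates, because the documents give no response distribution. The 693 forms are a loose ceiling: some patients may not have reached month 36, forms are collected before progression, and analysis requires a baseline form and a later one.

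E1 to E6 might be sequential database names for the six items. Variable names are not in the documents, so this cannot be excluded, but the same paragraph uses the form labels E7 and F2. Reading E1 as the unlabelled first question fails too, since that is the global item, scored separately, and E7 would still be lost.

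Finally, the hn12 line was read from text extracted from the PDF and should be confirmed on the page. The MDADI point does not depend on it.

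**Conclusion.** The concern holds: both rules are wrong as written, and no other part of the documents corrects them. Applied literally to complete forms, the MDADI emotional score is wrong by up to 16.7 of 100 points. With raw item 6, the H&N subscale, the TOI and the FACT-H&N total are wrong by up to 4 points in either direction. The MDADI missing-data result assumes that E1 counts as unanswered.

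Both are probably typing errors, and the intended rules can be recovered from the SAP and the forms. Whether any result is affected depends on the scoring program, which is not in the documents. The exposure is confined to Tables 19 and 20 and Figures 6 and 7; TOI has no named row in Table 19, so where it would be reported is not stated. The primary EFS analysis, the MDADI global, physical and functional scales, FOIS and PSS-HN are untouched. General pain still enters the TOI and the FACT-H&N total through item GP4. This should be fixed, but it does not threaten the trial's main conclusion.

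**What to change.** - SAP 2.8.1.3: define the emotional scale as E2 to E7, with E7 reversed.
- SAP 2.8.1.2: set the reversed item 12 to 4 minus the raw item 12, and compute every reversal from the raw item into a new variable so that line order cannot matter.
- Table 19 has a row for an MDADI total, for which 2.8.1.3 gives no formula. This is a separate omission: add the formula or delete the row, so that it is clear whether the emotional items feed into it.
- Check the scoring program against the corrected rules and record the check. If the literal lines were coded, rerun the affected rows of Tables 19 and 20 and the affected panels of Figures 6 and 7.

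The cost is two corrected lines, one formula added or one table row deleted, and a program check. No new data are needed.

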2.8.2 Analysis

All analyses on quality-of-life scores will include all eligible patients who have a measurement at baseline and at least one measurement after baseline.

2.8.2.1 Determination of assessment times

The following will be the scheme to determining the time frame of all QOL assessments (FACT, MDADI):

- 1) Baseline: Baseline evaluation is the QOL questionnaire collected closest, but prior to, the date of treatment started (usually within 2 weeks);
- 2) Last week of radiotherapy: If the QOL is assessed two weeks before or after the last week of radiotherapy, this assessment is considered as last week of radiotherapy assessment;
- 3) 3 months off treatment: If $2 \text{ weeks} < \text{or } = (\text{QOL assessed date} - \text{off treatment date}) < 4.5 \text{ months}$, this assessment is considered as 3 months assessment;
- 4) 6 months off treatment: If $4.5 \text{ months} < \text{or } = (\text{QOL assessed date} - \text{off treatment date}) < 9 \text{ months}$, this assessment is considered as 6 months assessment;
- 5) 12 months off treatment: If $9 \text{ months} < \text{or } = (\text{QOL assessed date} - \text{off treatment date}) < 18 \text{ months}$, this assessment is considered as 12 months assessment;
- 6) 24 months off treatment: If $18 \text{ months} < \text{or } = (\text{QOL assessed date} - \text{off treatment date}) < 30 \text{ months}$, this assessment is considered as 24 months assessment;
- 7) 36 months off treatment: $30 \text{ months} < \text{or } = (\text{QOL assessed date} - \text{off treatment date}) < 42 \text{ months}$, this assessment is considered as 36 months assessment;

Note: when there was multiple recode for the same patient within a given interval, the one that is closest to the nominal time point should be used for analysis.

2.8.2.2 Calculation of Compliance Rates

The compliance rate is calculated as the number of forms received out of the number of forms expected at each assessment point defined based on the following principles:

- 1) At baseline: the number of forms expected is the total number of patients who are administrated to the study and required to fill out QOL questionnaires.
- 2) Last week of radiotherapy: the number expected at last week of radiotherapy is the total number of patients who completed the radiotherapy treatment. If radiotherapy terminated early, complete QOL on last day of radiotherapy treatment or as soon as possible after radiation;
- 3) After protocol treatment: the number expected is the total number of patients who were alive at the time of assessment and have not withdrawn (consent) from the trial.

Compliance for FACT-HN and MDADI will be summarized in Table 18.

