Required Investigations	Pre-study	During Protocol Therapy (start of treatment until the end of RT)	After Protocol Therapy until Recurrence/Progression	Post Recurrence or Local, Regional or Distant Progression ¹
Correlative Studies				
Archival Tumour Tissues (for HPV genotyping and mutation testing)	Submit ≤ 4 weeks after registration			
Whole blood and plasma (for circulating cell free DNA [cffDNA])	After patient consent, prior to start of treatment		1 month post RT	
Radiomic analysis of protocol-mandated imaging	No additional investigations are required other than collection of protocol-mandated imaging (diagnostic, simulation/planning and relapse CT and/or MRI).			
Quality of Life				
FACT-H&N ¹⁰	≤ 14 days	Last week of RT	3, 6, 12, 24, 36 months post RT	
Swallowing Related Quality of Life				
MDADI	≤ 14 days	Last week of RT	3, 6, 12, 24, 36 months post RT	
Economic Analysis				
Health Utilities Index (EQ-5D-5L)	≤ 14 days	Last week of RT	3, 6, 12, 24, 36 months post RT	
Resource Utilization Assessment		Last week of RT	6, 12, 24, 36 months post RT	
Lost Productivity Questionnaire		Last week of RT	6 and 12 months post RT	
Swallowing Status				
FOIS	≤ 14 days	Last week of RT	3, 6, 12, 24, 36 months post RT	
PSS-HN	≤ 14 days	Last week of RT	3, 6, 12, 24, 36 months post RT	

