10.3 Follow-up Off Protocol Treatment

Please see Section 5.0.

For phase Ib and phase II studies, continued follow up after progression (on treatment or during follow up), using an abbreviated form (including subsequent therapies) every 6 months is required until CCTG advises centres that the final analysis has been performed and follow up can be discontinued. If patient is unable to return to participating centre for follow up, please contact CCTG to discuss possible options prior to considering 'withdrawal of consent' processes. Remote oversight allowing data submission may be feasible.

Final report (Form 6) will be required only on patients who die during protocol therapy, within 30 days after last dose, or within the protocol defined follow-up period for patients as above. Due within 2 weeks of knowledge of death (see Appendix III - Documentation for Study).

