EQ-5D-5L Questionnaire	
 • Prior to registration • Last week of radiotherapy • After RT (prior to PD): 3, 6, 12, 24 and 36 months 	On paper; site CRA to enter relevant data (as required) in the EDC system within corresponding folders	Retain questionnaires at the site
MDADI			
PRO-CTCAE			
Lost Productivity Questionnaire	
 • During the last week of RT • After RT (prior to PD): 6 and 12 months 		

* See Appendices V, VI, VII and VIII. If the questionnaire is completed on paper then it should be scanned and uploaded to the EDC Supporting Document Upload Tool.
			

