The only time that we will not require a patient to complete the quality of life questionnaires is if s/he does not understand either English or French. In other words, if the assistance of a translator is required to comprehend the questions and reply, the questionnaires should not be completed. Translation of the questions is not acceptable. Please indicate on questionnaire.

7. Unwillingness to Complete Quality of Life Questionnaire

If a patient speaks and reads English and/or French (or other languages that the questionnaires may be available in), but does not wish to complete the questionnaires then s/he is NOT eligible and should NOT be put on study.

8. Inability to Complete Quality of Life Questionnaire (for reason other than illiteracy in English or French)

An eligible patient may be willing but physically unable to complete the questionnaires, because of blindness, paralysis, etc. If the patient is completing the QOL assessment in the clinic, the questionnaire should be read to them and the answers recorded by a health care professional (e.g. preferably the clinical research associate assigned to the trial, but another clinic nurse, a doctor or social worker who is familiar with the instructions for administering the questionnaires would be acceptable). If the patient is completing the questionnaire at home, and a telephone interview by the clinical research associate is not possible, then a spouse or friend may read the questions to the patient and record the answers. However, this method should be a last resort, and the spouse or friend should be instructed to not coach or suggest answers to the patient. Whichever method is used, it should be recorded on the questionnaire.

If these special arrangements are not possible or feasible, then the patient would not be required to complete the questionnaires, and this should be reported on the appropriate case report form.

FACT Head & Neck

Quality of Life Questionnaire – ENGLISH

CCTG Trial: **HN.10**

This **page** to be completed by the Clinical Research Associate

Patient Information

CCTG Patient Serial No: _____

Patient Initials: _____

(first-middle-last)

Institution: _____

Investigator: _____

Scheduled time to obtain quality of life assessment: please check (✓)

Prior to registration Last week of radiotherapy

Post Radiotherapy Treatment, Prior to Progression

month 3 month 6 month 12 month 24 month 36

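### The SAP counts living patients who have progressed as owing QOL forms that most of the protocol schedules only before progression, so Table 18 can understate compliance at months 3 to 36

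*SAP*

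**What the plan says.** SAP 2.8.2.2 defines compliance as forms received over forms expected, with one rule for each period:

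- Baseline: "the total number of patients who are administrated to the study and required to fill out QOL questionnaires".
- Last week of radiotherapy: "the total number of patients who completed the radiotherapy treatment". The same item then asks patients who stop early to fill in a form on their last treatment day or soon afterwards.
- Visits once treatment has ended: "the number expected is the total number of patients who were alive at the time of assessment", leaving out anyone whose consent has been withdrawn.

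The results go into Table 18, which has Expected and Received columns for the eligible patients (n = 99).

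The protocol sets out when the forms are due:

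- Appendix III, in the timing entry for the questionnaires: "After RT (prior to PD): 3, 6, 12, 24 and 36 months".
- The FACT-H&N and MDADI cover pages offer months 3 to 36 only under the label "Post Radiotherapy Treatment, Prior to Progression".
- The Section 5.0 flowsheet puts the post-radiotherapy QOL visits in the column "After Protocol Therapy until Recurrence/Progression". The FACT-H&N and MDADI rows have no entry in the post-recurrence column.
- The Appendix V schedule table lists the same visits without mentioning progression.

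Section 10.3 keeps progressed patients in the study: "continued follow up after progression (on treatment or during follow up), using an abbreviated form (including subsequent therapies) every 6 months is required".

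**The concern.** A compliance rate should compare the forms returned with the forms that were due. Under the post-treatment rule, a patient who has progressed, is alive and has not withdrawn adds one to the denominator. If the site follows the prior-to-progression schedule, that patient adds nothing to the numerator. Table 18 would then mix forms that stopped by design with forms that were missed, and the mixture grows at later visits as more patients progress.

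The post-treatment rule also omits the baseline rule's restriction to patients who are required to complete the questionnaires. The protocol admits patients who cannot complete them (Section 4.1.6) and waives them for patients who understand neither English nor French (Appendix V). Such patients would leave the denominator at baseline and re-enter it at month 3.

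QOL is a secondary objective and part of the rationale for reducing the treated volume. Compliance is what a reader uses to judge how far missing forms limit the QOL results.

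**Working it through.** **Comparing the rules.** The plan states no compliance figure, so there is none to reproduce. The SAP's conditions are alive and not withdrawn. The conditions in Appendix III, the cover pages and the flowsheet amount to those two plus progression-free. The patients who meet the first set but not the second are the living progressed patients, and Section 10.3 keeps them under follow-up.

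**Sizing the effect.** Inputs:

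- 2-year EFS of 91% (Ha) and 85% (H0), from SAP 1.2. EFS is a proxy for progression; its events other than death are progression or recurrence, metastasis, surgery with tumour present or unknown, and non-protocol therapy without a documented site of failure.
- Constant hazard (assumption). It agrees with the plan's own decision rule: 18 events in 304.7 person-years give exp(−2 × 18/304.7) = 88.86%, against the stated 88.85%.
- Radiotherapy ends about 2 months after registration (assumption), so month m after radiotherapy is m + 2 months after registration.
- f, the share of EFS failures alive at the visit. The documents do not give it; the assumed range is 25% to 100%.
- No withdrawals, and every form due before progression is returned (assumption).

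Formulas: S = (2-year EFS)^((m + 2)/24). Highest compliance the rule can show = S / [S + f(1 − S)].

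Month 24, EFS 91%: S = 0.91^(26/24) = 0.903.
- f = 1: 0.903/(0.903 + 0.097) = 90.3%.
- f = 0.25: 0.903/(0.903 + 0.024) = 97.4%.

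Month 24, EFS 85%: S = 0.85^(26/24) = 0.839.
- f = 1: 83.9%.
- f = 0.25: 0.839/(0.839 + 0.040) = 95.4%.

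| Month after RT | S, EFS 91% | Highest compliance | S, EFS 85% | Highest compliance |
|---|---|---|---|---|
| 3 | 0.981 | 98.1–99.5% | 0.967 | 96.7–99.1% |
| 12 | 0.947 | 94.6–98.6% | 0.910 | 91.0–97.6% |
| 24 | 0.903 | 90.3–97.4% | 0.839 | 83.9–95.4% |
| 36 | 0.861 | 86.1–96.1% | 0.773 | 77.3–93.2% |

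With the denominator limited to progression-free patients, each entry would be 100%. The shortfall is therefore 0.5–3.3 points at month 3, 2.6–16.1 at month 24 and 3.9–22.7 at month 36.

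In patients, 99 × f × (1 − S) at month 24 is 2.4 to 9.6 under 91% EFS and 4.0 to 16.0 under 85%. These counts take all 99 as having reached the visit; the percentages do not depend on that.

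**Last week of radiotherapy.** The denominator is completers, while early stoppers are also asked for a form. If their forms are counted as received, the numerator includes patients who are not in the denominator and the rate rises. The SAP does not say whether they are counted.

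**The case against.** The best counter-argument is that the protocol is not uniform. The Appendix V schedule table gives months 3 to 36 without a progression limit. Its instructions name lack of English or French as the only ground for waiving the forms, with a further item on physical inability. Read alone, Appendix V is compatible with the SAP rule, and the shortfall shrinks if sites collect forms after progression. This stands as a limit on the size. It does not remove the mismatch, because Appendix III, both cover pages and the flowsheet all point to collection before progression.

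A second argument is that all living patients is a legitimate, conservative denominator. It can describe how much data exists among survivors. But Table 18 is labelled as received over expected, and the baseline rule counts only patients required to complete the forms.

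A third argument is that little depends on the rate. That is correct. The QOL analysis is descriptive; no test or inclusion rule uses compliance. The score summaries take eligible patients with a baseline and at least one later measurement (SAP 2.8.2). Table 18 also prints the counts, although not split by progression.

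The text on contacting patients who no longer attend clinic, in Appendices VII and VIII, concerns the Lost Productivity and EQ-5D-5L forms and does not alter the schedule for FACT-H&N and MDADI.

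**Conclusion.** The mismatch is real and minor. At months 3 to 36, Table 18 understates compliance whenever living patients have progressed and their forms are not collected. Under the stated assumptions, the highest compliance it could show is about 84–97% at month 24 and 77–96% at month 36. The width of these ranges reflects the unknown number of living progressed patients. A narrower range would need an overall-survival figure that the documents do not give. The effect of dropping the required-to-complete condition cannot be sized, because the number of exempt patients is not given.

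A reader might infer more than the documents support:

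- That every living patient is counted. Patients who withdrew consent are excluded.
- That compliance is too low at every time point. Baseline has its own rule, a mismatch at the last week of radiotherapy would raise the rate, and the shortfall is zero at any visit where no living patient has progressed.
- That the QOL results themselves are distorted. The score tables do not use the compliance rate, and the primary analysis is untouched.

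**What to change.** In SAP 2.8.2.2, define expected post-treatment forms as those of eligible patients who are required to complete the questionnaires and who, at the scheduled visit, are alive, not withdrawn and progression-free. Add to Table 18, for each visit, the number no longer due because of progression. State that the prior-to-progression schedule governs, since Appendix V does not say so, and count a form received after progression in neither numerator nor denominator.

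For the last week of radiotherapy, use the same patients in both parts of the fraction: either completers only, or all who started radiotherapy.

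The cost is SAP wording and one added column. Progression is already recorded on the Relapse/Progression Report (Appendix III), so no new data are needed.
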